9.6.6. Bisphosphonates and RANK-L Targeted Agents

Patients with bone metastases present on baseline imaging should be appropriately treated with bisphosphonates or RANK-L targeted agents (for example, denosumab), per respective approved labels. Initiation of treatment with bone-modifying agents must begin at least 7 days prior to randomization. Patients receiving bisphosphonates or RANK-L targeted agents should not switch treatments (for example, replace a bisphosphonate with denosumab) while on study treatment. However, exceptional cases without evidence of PD may be considered in consultation with the Lilly CRP. These exceptional cases will not incur a protocol deviation.

9.7. Treatment Compliance

Treatment compliance information for study treatment will be collected through patient dosing diaries and/or capsule/tablet counts at each visit, with the number of capsules/tablets taken relative to the number expected to be taken summarized for each cycle. The patient must take ≥75% of the planned doses for study treatment in a cycle to be deemed compliant. As outlined in Section 9.4.1.1.2, dose suspensions or delays may occur and will not result in a patient being considered as noncompliant. A patient may be considered noncompliant if she is judged by the

investigator to have intentionally or repeatedly taken \geq 125% of the planned doses of study treatment in a cycle.

Importantly, a patient who receives surgery \pm radiotherapy for locoregionally recurrent breast cancer is not considered noncompliant and does not incur a protocol deviation. For additional information, refer to Section 9.6.1.

Potential discontinuation of a patient due to study drug noncompliance will be discussed the investigator and the Lilly CRP before any determination is made to discontinuation.

9.7.1. Patient Diaries

The study will include patient diaries to provide dosing instructions, help patients are reatment planning, and track actual doses of study treatment taken by the patient. It formation from the diaries may be used for documenting study treatment compliance as well a dosing time relative to PK blood draws and ECG collection.

10. Efficacy, Health Outcome/Quality-of-Life Measures, Safety Evaluations, Sample Collection and Testing, and Appropriateness of Measurements

Written informed consent must be obtained prior to any study-specific pretreatment evaluations.

Study procedures related to efficacy, safety, health outcome/quality-of-life measures, sample collection and testing assessments and their timing are described in the sections below and shown in the Study Schedule (Attachment 1).

10.1. Efficacy Measures

10.1.1. Efficacy Assessments at Baseline and during Study Treatment

Within 28 days of randomization, baseline tumor assessments will be performed for each patient. The method of assessment used at baseline must be used consistently for serial tumor assessment throughout the study. Bone scintigraphy will be performed for all patients at baseline (within 28 days of randomization). However, prior bone scintigraphy (obtained as part of routine clinical care) within 45 days before Day 1 of Cycle 1 is also acceptable. All tumor assessment images must be submitted for central review.

For all patients, imaging studies (computed tomography [CT], including spiral CT, or magnetic resonance imaging [MRI] scan of the chest, abdomen, and pelvis) will be performed locally at baseline and repeated between Day 21 and Day 28 of every second cycle beginning with Cycle 2 and continuing through Cycle 18 (inclusive), between Day 21 and 28 of every third cycle after Cycle 18, and within 14 days of clinical progression per the Study Schedule (Attachment 1). It is recommended that CT imaging of the abdomen and pelvis be performed with IV contrast, whenever possible. For patients with known hypersensitivity to CT contrast material, a CT scan of the chest without contrast and gadolinium-enhanced MRI of the abdomen and pelvis are encouraged. The CT portion of a positron emission tomography (PET)-CT scan may be used as a method of response assessment if the site can document that the CT is of identical diagnostic quality to a diagnostic CT (with IV and oral contrast). A PET scan alone or as part of a PET-CT may be performed as part of routine clinical care but cannot be used to assess response according to RECIST v1.1.

For all patients, bone scintigraphy will be performed locally at baseline and repeated between Day 21 and Day 28 of every sixth cycle beginning with Cycle 6. In addition, bone scans should be repeated even if a complete response in target disease is identified or progression in bone is suspected. For patients with new lesions identified by post-baseline bone scintigraphy, targeted assessment by X-ray, CT scan with bone windows, or MRI will be performed to confirm findings.

For only those patients with bone lesions identified by bone scintigraphy at baseline, directed imaging using one of the following methods will be performed at baseline: X-ray, CT scan with bone windows, or MRI. Directed imaging using the same method as at the baseline bone lesion

assessment should be repeated between Day 21 and Day 28 of every second cycle beginning with Cycle 2 and continuing through Cycle 18 (inclusive), between Day 21 and Day 28 of every third cycle after Cycle 18, and within 14 days of clinical progression.

For patients with locoregionally recurrent breast cancer not amenable to curative treatment, MRI scan of the breast will be performed at baseline, if applicable. Breast MRI, if applicable, will be repeated between Day 21 and Day 28 of every second cycle beginning with Cycle 2 and continuing through Cycle 18 (inclusive), between Day 21 and Day 28 of every third cycle after Cycle 18, and within 14 days of clinical progression.

For patients with visible tumor (such as skin lesions), photography will be performed at baseline and each photographic image of the tumor should include a ruler. Photography should be repeated on Day 1 of every second cycle beginning with Cycle 3 and continuing through Cycle 19 (inclusive), on Day 1 of every third cycle after Cycle 19, and within 14 days of clinical progression. Photographic images may be taken more frequently based upon the discretion of the investigator or following the identification of new skin lesions post-baseline.

For patients continuing treatment during the Continued Access Period (after study completion), efficacy assessments (frequency and type of assessments) will be at the discretion of the investigator.

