9.3. Method of Assignment to Treatment

Upon obtaining informed consent, site personnel should access the interactive web response system (IWRS) which will assign a patient number. Patients who meet all criteria for enrollment will be randomly assigned to receive either LY2835219 or placebo. Assignment to treatment groups will be determined by a computer-generated random sequence using the IWRS. Sites will be prompted to enter the specific NSAI at time of randomization.

Randomization will be stratified by the following: nature of disease (visceral metastases versus bone-only metastases versus other), and prior (neo)adjuvant endocrine therapy (aromatase inhibitor therapy versus other versus no prior endocrine therapy).

The IWRS will be used to assign LY2835219 or placebo and distribute NSAI supplied by Lilly. Site personnel will confirm that they have located the correct study medication packages by entering a confirmation number found on the packages into the IWRS.

The period between randomization to blinded study drug and the first dose (Cycle 1, Day 1) should not exceed 7 days.

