9.4. Selection and Timing of Doses

Blinded study drug will be taken orally every $12 (\pm 2)$ hours on Days 1 through 28 of a 28-day cycle, for a total of 56 doses per cycle. During all cycles, blinded study drug should be taken at approximately the same times each day. If a patient misses or vomits a blinded study drug dose, that dose should be omitted.

Anastrozole or letrozole will be administered orally every 24 hours (±2) on Days 1 through 28 of a 28-day cycle for a total of 28 doses per cycle. For PK and electrocardiogram (ECG) purposes, anastrozole or letrozole should be administered at the same time as (or up to 20 minutes after) the morning dose of blinded study drug through Cycle 4, Day 1. Subsequently, the interval between administration of blinded study drug and anastrozole or letrozole may be adjusted based on the judgment of the investigator. If a patient misses or vomits an anastrozole or letrozole dose, that dose should be omitted.

A cycle is defined as an interval of 28 days plus any subsequent delay prior to start of the next cycle. A delay in the start of a cycle due to holidays, weekends, bad weather, or other unforeseen circumstances will be permitted up to 7 days and not counted as a protocol deviation). For each 28-day cycle, a total of 56 doses of blinded study drug will be dispensed. In exceptional cases, for planned delays (including but not limited to vacation or holidays), additional study treatment may be dispensed.

A patient may continue to receive study treatment until she meets 1 or more of the specified reasons for discontinuation (as described in Section 7.3.1).

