9.4.1.1.2. Dose Suspension (within a Cycle) and Cycle Delay

Both dose suspension (within a cycle) and cycle delay are permitted. When a dose suspension or cycle delay occurs related to toxicity (defined as an AE possibly related to study treatment per

investigator judgment), the blinded study drug and/or NSAI may be suspended or delayed as determined by the investigator's judgment.

Study treatment may be held up to 14 days within a cycle or at start of next cycle to permit sufficient time for recovery from the toxicity. If a dose suspension occurs within a cycle, the investigator may resume blinded study drug dosing at the same dose level for the remainder of the cycle or at reduced dose (assuming resolution to at least Grade 1 for non-hematological and at least Grade 2 for hematological toxicity). If the patient experiences the same toxicity with the same or greater severity (CTCAE grade) requiring a dose suspension within a cycle or at start of the next cycle, the patient must be dose reduced and not re-challenged a second time at the prior dose level

Patients not recovering from toxicity within 14 days should be considered for discontinuation of the blinded study drug and/or co-administered NSAI. In exceptional circumstances, a delay >14 days is permitted upon agreement between the investigator and the Lilly CRP and blinded study drug dose adjustment is to be considered.

In the event of a cycle delay due to logistical reasons (for example, due to patient availability), the patient should continue on study treatment if the patient has adequate drug supply. If a patient's treatment is interrupted as a result of not having sufficient drug supply, the cycle may be delayed up to 7 days (and not be considered a protocol violation). In exceptional circumstances, a delay >7 days is permitted upon agreement between the investigator and the Lilly CRP.

The start of a cycle may be delayed, or a current cycle interrupted, to allow a patient with a locoregionally recurrent breast cancer rendered operable by study treatment to receive surgery \pm radiotherapy. For additional information, refer to Section 9.6.1.

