9.4.1.1.3. Hematologic Toxicity

If a patient experiences Grade 4 hematologic toxicity, then dosing must be suspended (until the toxicity resolves to either baseline or at least Grade 2) and the dose of blinded study drug must be reduced by one dose level as outlined in Table JPBM.9.2.

If a patient experiences Grade 3 hematologic toxicity, then dosing must be suspended (until the toxicity resolves to either baseline or at least Grade 2) and the dose of blinded study drug may be reduced by one dose level as outlined in Table JPBM.9.2 at the discretion of the investigator.

Before the start of each cycle, hematologic toxicity must resolve to either baseline or at least Grade 2.

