9.4.1.1.4. Nonhematological Toxicity

If a patient experiences ≥Grade 3 nonhematologic toxicity, then blinded study drug and/or NSAI dosing must be suspended (until the toxicity resolves to either baseline or at least Grade 1) and the dose of blinded study drug must be reduced by one dose level as outlined in Table JPBM.9.2.

If a patient experiences persistent or recurrent Grade 2 nonhematologic toxicity (except diarrhea; refer to Section 9.4.1.1.4.1) that does not resolve with maximal supportive measures within 7 days to either baseline or at least Grade 1, then blinded study drug and/or NSAI dosing may be suspended (until the toxicity resolves to either baseline or at least Grade 1) and the dose of blinded study drug may be reduced by one dose level as outlined in Table JPBM.9.2 at the discretion of the investigator.

Before the start of each cycle, nonhematologic toxicity (except alopecia and fatigue) must resolve to either baseline or at least Grade 1.

9.4.1.1.4.1. Diarrhea

A patient experiencing diarrhea requiring hospitalization (irrespective of grade, that is, requiring intravenous [IV] rehydration) or severe diarrhea (Grade 3 or 4; see Attachment 9) must have study treatment suspended (until the toxicity resolves to either baseline or at least Grade 1) and must have the blinded study drug dose reduced by one dose level as outlined in Table JPBM.9.2.

If a patient experiences persistent or recurrent Grade 2 diarrhea that does not resolve with maximal supportive measures (refer to Section 9.6.5) within 3 days to either baseline or at least Grade 1, then study treatment should be suspended (until the toxicity resolves to either baseline or at least Grade 1) and the dose of blinded study drug may be reduced by one dose level as outlined in Table JPBM.9.2 at the discretion of the investigator. If the same dose level was resumed and diarrhea recurs despite maximal supportive measures, the dose of blinded study drug must be reduced by one dose level as outlined in Table JPBM.9.2.

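### On-treatment imaging follows cycle number, so if cycle delays are more frequent on LY2835219 (an assumption) the PFS log-rank test tilts slightly toward it

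*Protocol*

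**What the plan says.** **On treatment, the clock is the cycle number.** Protocol Section 10.1.1 has CT/MRI "repeated between Day 21 and Day 28 of every second cycle beginning with Cycle 2 and continuing through Cycle 18 (inclusive", and every third cycle after that. Directed bone imaging and breast MRI follow the same pattern. Bone scintigraphy falls between Day 21 and "Day 28 of every sixth cycle beginning with Cycle 6". For visible tumor, "Photography should be repeated on Day 1 of every second cycle beginning with Cycle 3 and continuing through Cycle 19 (inclusive". Attachment 1 repeats these rules.

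**The cycle can stretch.** Protocol Section 9.4: "A cycle is defined as an interval of 28 days plus any subsequent delay prior to start of the next cycle". Section 9.4.1.1.2: "Study treatment may be held up to 14 days within a cycle or at start of next cycle", with longer delays possible by agreement with the sponsor's physician. Sections 9.4.1.1.3 and 9.4.1.1.4 make the next cycle wait for recovery: "Before the start of each cycle, hematologic toxicity must resolve to either baseline" or Grade 2, and "Before the start of each cycle, nonhematologic toxicity (except alopecia and fatigue) must resolve to either baseline or at least Grade 1". A start-of-cycle delay therefore moves all later on-treatment scans. A suspension within a cycle that resolves in time does not.

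**Off treatment, the clock is randomization.** Section 10.1.2 and Attachment 1 set imaging about 8-weekly to 18 months after randomization and about 12-weekly from then on. Off-treatment bone scans are about 6-monthly.

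**Analysis.** SAP Table JPBM.6.1 dates a documented progression at the assessment that showed it. SAP Section 6.7.2.2 tests PFS by stratified log-rank. None of the four sensitivity analyses in SAP Section 6.7.5.1 concerns scan timing that differs by arm; the third only moves progressions found at unscheduled scans forward to the next scheduled one.

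**The concern.** Progressions cluster around scans and are dated there. If control patients are scanned some days earlier than LY2835219 patients, the control events in each cluster are counted while LY2835219 patients with the same disease status are still in the risk set as event-free. With no true effect, that ordering tilts the log-rank statistic toward LY2835219.

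Average PFS barely changes. Some progressions are dated later because the scan is late. A patient who progresses between the nominal and the delayed scan is found sooner than at the next nominal scan. What remains is an effect on ordering. At stake is a small, avoidable excess of one-sided error in the primary test, in the direction that favors the experimental arm.

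**Working it through.** **1. The plan's own figures reproduce.**
- Protocol events: (1.960 + 0.842)² / [(2/9) × (ln 0.714)²] = 7.849 / 0.02522 = 311.2, so 312, as in Protocol Section 12.1.
- SAP power at 240 events and HR 0.67: √(240 × 2/9) = 7.303; 7.303 × 0.4005 − 1.960 = 0.965, giving 83.3%, consistent with SAP Section 5.2.
- SAP final boundary, with 0.00025 spent at 189 of 240 events: 0.0249993, as stated.
- Critical observed HR at 240 events: exp(−1.960 / 7.303) = exp(−0.268) = 0.765.

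**2. Separation of scan dates.** Seventeen cycle starts (Cycles 2 to 18) precede the Cycle 18 scan. The mean separation is 17 × 7 days × the difference in delay rates:
- 10% v 5%: 17 × 7 × 0.05 = 6 days
- 10% v 2%: 17 × 7 × 0.08 = 10 days
- 20% v 5%: 17 × 7 × 0.15 = 18 days

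**3. Null simulation.**
- From the documents: 300:150 patients; exponential PFS with a 10-month median (used in both arms); the Section 10.1.1 scan cycles; a 0-7 day first-dose gap ("The period between randomization to blinded study drug and the first dose (Cycle 1, Day 1) should not exceed 7 days"); scans within 14 days of clinical progression; the 30-day follow-up visit and calendar imaging after discontinuation; analysis at 240 events; one-sided 0.025.
- Assumed: the delay rates above; 15-month uniform accrual; a 1-7 day logistical delay in 10% of cycles in both arms; 15% of progressions found off schedule; 5% deaths dated exactly; exponential discontinuation with mean 40 months. The log-rank test was unstratified.
- Cases were simulated separately with 12,000 to 40,000 runs each (Monte Carlo SE about 0.1-0.15 point). Ranges span those simulations.

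| Case (LY2835219 v placebo) | Null one-sided error | HR |
|---|---|---|
| No toxicity delay | 2.5-2.8% | about 0.996 |
| Equal delays | 2.7-2.8% | |
| 10% v 5% | 3.0-3.2% | 0.989-0.990 |
| 10% v 2% | 3.3-3.4% | 0.984 |
| 20% v 5% | 3.0-3.6% | 0.980-0.984 |
| Same three pairs, delays concentrated in some patients and 30% found off schedule | 2.8-3.1% | 0.991-0.995 |
| Imaging anchored to randomization | 2.5-2.7% | |

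Variants at 20,000-40,000 runs: earlier discontinuation on LY2835219 (mean 30 v 120 months) gave 3.0%, 3.2% and 3.4% for the three pairs, against 2.9% with anchored imaging. Adding delay rates halved after Cycle 6 gave 2.8%, 3.2% and 3.4%. The highest value in any variant was 3.8% (rising hazard, 20% v 5%).

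**4. Drift due to delays.** The no-delay HR is already about 0.996, so the fair comparison is with that and not with 1. For the largest set of runs, 0.990/0.996, 0.984/0.996 and 0.980/0.996 give 0.6%, 1.2% and 1.6%. The simulation that supplied the 0.996 put the drift at about 0.2-1.2%. Taken together, roughly 0.2-1.5%. Against the log-HR of 0.268 needed for significance, that is 0.002/0.268 to 0.015/0.268, or about 1-6%. A 1.5% drift could change the conclusion only for an observed HR between about 0.765 × 0.985 = 0.753 and 0.765.

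**5. Other analyses.** The restricted mean test of SAP Section 6.7.2.3.2 stayed at 2.6-2.9% in every unequal-delay case, and its mean difference moved by at most 0.6 day. An interval-censored proportional hazards model with a piecewise-exponential baseline gave 2.7%, 2.6% and 2.7%, and 2.5% in all three pairs under a Weibull hazard (shape 1.3). Each of these two results rests on a single simulation.

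**The case against.** The strongest case against has four parts.

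- **The premise is undocumented.** Neither document gives a start-of-cycle delay rate for either arm, and with equal delays nothing happens. Section 9.4.1.1.2 also limits repetition, because recurrence of the same toxicity at the same or greater grade that needs a suspension leads to dose reduction. This stands. The common events named in the Protocol introduction make unequal delays plausible but do not measure them.
- **The size depends on modelling choices.** If delays concentrate in some patients and more progressions are found off schedule, the excess over equal delays falls to a few tenths of a point or less, and the fix gains close to nothing. This stands and sets the low end of the range.
- **Much is already planned.** Dose delays are summarized by arm (Protocol Sections 12.2.5 and 12.2.12), the data monitoring committee sees them (SAP Section 6.14.1), and the restricted mean difference is prespecified. This stands in part. The summaries would reveal unequal delays but do not correct scan timing in the log-rank test. The SAP does not link the restricted mean to scan timing. Central review reads the same scans.
- **The text may be superseded.** The imaging schedule is from the September 2014 protocol and the 240 events from the April 2017 SAP. Amendments (a) and (b) were not supplied. This stands.

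A reader might infer that the error roughly doubles, to about 5%. A model without deaths, off-schedule scans and calendar imaging after discontinuation does give 3.5-5.5%. The protocol provides for all of these, so those figures do not describe this trial. A reader might also take the 25.7% v 13.6% Grade 3 diarrhea rates in the Protocol introduction as evidence of unequal delays. They compare combination with single-agent use at 200 mg, with no placebo arm, and are not cycle delays.

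**Conclusion.** The point holds as a small design weakness. The documents establish the mechanism: cycle-tied scans, cycles that lengthen with delay, and a randomization clock only off treatment. They do not establish that delays differ by arm. If 7-day start-of-cycle delays occur in 10% v 5%, 10% v 2% or 20% v 5% of cycles, the null one-sided error is about 2.8-3.6% against about 2.7% with equal delays or anchored imaging, an excess of about 0.1-0.9 point. The drift is small beside the design HR of 0.67 and matters only for a borderline PFS result.

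It would be wrong to conclude that the plan contradicts itself or that the PFS gain would be materially overstated in months. The text is consistent, and the simulated mean difference hardly moves. The conclusion rests on the assumed delay rates and simulation settings, and on Section 10.1.1 still reading as in the supplied protocol.

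**What to change.** **Preferred.** In Protocol Section 10.1.1 and Attachment 1, schedule on-treatment CT/MRI, directed bone imaging, breast MRI and photography in weeks from randomization, regardless of cycle delays. Use the Section 10.1.2 clock: about every 8 weeks to 18 months, then about every 12 weeks. Schedule bone scintigraphy about every 24 weeks (6 × 28 days = 24 weeks, close to the off-treatment interval). Keep the scan within 14 days of clinical progression. No dosing rule changes.

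**Cost.** Amendment wording, and some scans that no longer coincide with a delayed cycle visit. Anchoring gives 72/8 = 9 scans by week 72, against a simulated 8.0-8.4 on the cycle-tied schedule. That is no more often in calendar time than the undelayed plan.

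**If the schedule cannot change, or the amendments have already changed it.** Add to SAP Section 6.7.5.1 an interval-censored PFS sensitivity analysis on actual scan dates, with a by-arm table of scan times and intervals. State that both will be read alongside the restricted mean difference of SAP Section 6.7.2.3.2. The cost is SAP wording, one table and one model. If scan timing proves balanced, the table settles the question.
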